2.3 Preliminary Data

Our Tanzanian colleagues conducted a preliminary study with similar research design over 12 months from March 2013 to February 2014. Fifty-four patients with Gustilo and Anderson Type 3A tibial shaft fractures were enrolled and randomly allocated to two treatment groups. Twenty six were treated with definitive external fixation, and 28 were managed with intramedullary nailing. Two patients were lost to follow-up from each group, leaving a total study population of 50 patients followed for 4.5 months.

As previously stated, the most common mechanisms of injury included motorcycle collisions (75.8%) and motor vehicle collisions (20.4%), followed by bicycle accidents and falls from height (combined 3.8%). Young men were most commonly affected. More than 60% of patients were treated within 16 hours from injury and 98% were treated within 24 hours from time of injury. Patients were treated according to standard open fracture protocols and randomized to two treatment groups undergoing either intramedullary nailing or external fixation.

We found no statistically significant difference in the rates of wound healing or incidence of deep infection (7.7% for IMN vs 12.5% for ex-fix). Twelve patients (46.2%) treated with external fixators developed superficial infection, none of which required implant removal. We observed a significantly faster time to callus formation in the intramedullary nail group (average 8.15 +/- 2.5 weeks, 92% at 10 weeks) when compared with the external fixation group (14.7 +/- 3.3 weeks, 25% at 10 weeks). Patients treated with intramedullary nails attained full weight bearing earlier than pts treated with external fixators. Malunion rates were also significantly lower in the intramedullary nail group, as two ex-fix patients (8.3%) were found to have significant post-operative limb length discrepancies and three (12.5%) were revised for angular or rotational malalignment, versus no malunions noted in the intramedullary nail group.

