In summary, 9 patients (37.5%) treated with external fixation required re-operation (2 for deep infection, 3 for malalignment, 4 for delayed union) versus one re-operation (3.8%) for patients treated with intramedullary nailing. While early results from this pilot study predict a clinical advantage for intramedullary nailing over definitive external fixation, we feel the small sample size, limited follow-up, and lack of functional outcomes data warrant further empirical investigation. Most importantly, this pilot study, conducted by a Tanzanian primary investigator, demonstrates the viability of success for completing a larger randomized, prospective clinical trial in Dar es Salaam, Tanzania.

3. Specific Aims

Study Objective: To determine the optimal management of severe open tibial fractures in Sub-Saharan Africa in order to reduce long-term disability, limit the economic impact of injury, and avoid resource costs of reoperation.

Specific Aims

1) Compare the all-cause reoperation rate for AO/OTA Type 42 open tibial shaft fractures treated with initial intramedullary nailing versus external fixation at Muhimbili Orthopaedic Institute in Dar es Salaam, Tanzania.

- 2) Compare rates of secondary clinical endpoints including postoperative superficial and deep infection, clinical union, radiographic union, malunion, and health-related quality of life with minimum one year follow-up.
- 3) Identify prognostic factors related to the patient, injury, or management protocol that impact the reoperation rate, return to work, and health-related quality of life.

Study Null Hypothesis: There is no difference in the all-cause re-operation rate comparing reamed intramedullary nailing and external fixation for the initial treatment of OTA 42 Type 42 open tibia fractures

4. Methods

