4.1 Outcomes

The primary outcome for our study will be composite, all-cause reoperation within one year of definitive skeletal stabilization, excluding bedside irrigation and debridement for superficial pin tract infections or planned ex-fix removal. The use of composite outcomes has been validated in a wide range of clinical trials.¹⁹ Primary events included in our composite outcome are detailed in the following table.

A participant who undergoes conversion from ex-fix to nail within six weeks of surgery will be analyzed according to the initial treatment that was assigned by randomization. Patients who undergo conversion from ex-fix to nail more than six weeks after the index procedure will be considered to have undergone a reoperation and will therefore count toward the primary outcome. Conversion from nail to ex-fix, regardless of time point, will be considered a primary outcome event.

Primary Events

Infection or hematoma	Repeat incision and debridement or drainage for superficial or deep infection or hematoma following initial wound healing.
Bone grafting	Bone grafting for patients > 6 months from index surgery. Bone grafting will be considered after 6 months in the case of delayed radiographic healing with > 2 months pain on attempted weight bearing.
Implant conversion (e.g. Ex Fix to IM nail) or implant exchange (e.g. exchange nailing)	Implant conversion or implant exchange > 6 months from index surgery to facilitate union.
Implant removal	
 1) For construct failure with appropriate clinical indication (broken hardware, half-pin failure at bone/pin interface). 2) Intramedullary nail removal to facilitate union. 3) Intramedullary nail removal due to patient reported pain or local irritation
Dynamization of intramedullary nail	
To facilitate healing > 6 months from index surgery.
 
* Note: Auto-dynamization without clinical indication for removal of broken component will not be counted as a primary event.

Osteotomy	To correct malalignment
Amputation	For limb salvage failure

Secondary clinical outcomes will include:

1. Post-operative compartment syndrome.
2. Superficial infection, as defined by CDC surveillance definitions, to include pin tract infections and cellulitis which resolves with use of antibiotics and local wound care.
3. Deep infection, as defined by CDC surveillance definitions, to include deep abscess or osteomyelitis.

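### Section 4.1 gives two counting rules for implant conversion in the primary outcome, six weeks in the text and six months in the table, and does not say which governs

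*Protocol*

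**What the plan says.** Protocol section 4.1 opens by defining the primary outcome as "composite, all-cause reoperation within one year of definitive skeletal stabilization, excluding bedside irrigation and debridement for superficial pin tract infections or planned ex-fix removal". Aim 1 in section 3 has the same scope: "Compare the all-cause reoperation rate for AO/OTA Type 42 open tibial shaft fractures". The null hypothesis is also stated for all-cause reoperation.

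Section 4.1 then introduces a table: "Primary events included in our composite outcome are detailed in the following table". Before the table come specific rules for conversion:

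- From external fixator to nail: "Patients who undergo conversion from ex-fix to nail more than six weeks after the index procedure will be considered to have undergone a reoperation", and the text adds that these count toward the primary outcome. No reason for the conversion is required.
- From external fixator to nail within six weeks: the patient is analysed in the randomised arm. Whether the conversion is itself an event is not said.
- From nail to external fixator: "Conversion from nail to ex-fix, regardless of time point, will be considered a primary outcome event".

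The table has a row for implant conversion or exchange, with ex-fix to nail and exchange nailing as its examples. It reads: "Implant conversion or implant exchange > 6 months from index surgery to facilitate union". A separate row on implant removal includes "Intramedullary nail removal to facilitate union", with no time limit.

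**The concern.** The two rules cover the same operation with different time limits and different conditions on purpose. The window between them runs from six weeks to six months, about 20 of the 52 weeks of follow-up. It contains the 3-month visit at which the external fixator plan is decided (section 5.7). Removal is the standard plan at that visit, but the follow-up form in section 6.5 lists conversion under its Other option.

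The disputed ex-fix-to-nail events can arise only in patients with an external fixator, so the choice of rule can change the between-arm difference. Adjudication takes place every two months during the trial (section 5.10), and all co-investigators review interim analyses every six months (section 4). A rule settled late may be settled by people who have seen results by arm.

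**Working it through.** **1. The rules side by side (section 4.1)**

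| Operation | Text | Conversion/exchange row | Other rows |
|---|---|---|---|
| Ex-fix to nail, within 6 weeks | Analysed as randomised; event status not stated | Not counted | Depends on reason |
| Ex-fix to nail for union, 6 weeks to 6 months | Event | Not counted | No row clearly applies |
| Ex-fix to nail for union, after 6 months | Event | Event | – |
| Ex-fix to nail for another reason, after 6 months | Event | Not counted | Depends on reason |
| Nail to ex-fix, before 6 months | Event | Not counted | May match implant removal or infection |
| Exchange nailing for union, before 6 months | No specific rule; all-cause wording would count it | Not counted | Can match implant removal |

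The second line is a direct conflict. The last two depend on which row the adjudicator reads.

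**2. Is there a precedence rule?** None was found. Section 5.10 has three steering committee members vote on whether an event is a primary outcome, with no threshold. The dated clarifications in section 1 do not address the point.

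**3. Weight of one event.** Section 4.2 plans 88 per group with completed follow-up and projects 192 analysed, or 96 per group. One reclassified event moves its arm by 1/88 = 1.1 points, or 1/96 = 1.0 point.

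**4. The planned sample size.** Inputs are 5% versus 20%, 80% power and alpha 0.05. Section 4.2 does not state sidedness; two-sided is taken here.

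- n0 = [1.960·√(2·0.125·0.875) + 0.842·√(0.05·0.95 + 0.20·0.80)]² / 0.15² = 75.1
- With continuity correction: n = (n0/4)·[1 + √(1 + 4/(n0·0.15))]² = 87.9, so 88

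The stated 88 reproduces. Section 4.2 does not say which counting rule its 20% assumes. Suppose w points of that 20% are patients whose only event is a disputed conversion, those events do not count, and the nail rate stays at 5%. The protocol gives no value for w.

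| w (points) | Ex-fix rate | n per group | Power at 88 per group |
|---|---|---|---|
| 0 | 20% | 88 | 80% |
| 2 | 18% | 109 | 70% |
| 5 | 15% | 160 | 50% |
| 8 | 12% | 276 | 28% |

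**5. Illustration from the pilot (section 2.3).** After losses the arms are 26 − 2 = 24 ex-fix and 28 − 2 = 26 nail, "leaving a total study population of 50 patients followed for 4.5 months". Ex-fix reoperations were 9/24 = 37.5%. Four were for delayed union, the largest single reason: 4/24 = 16.7%, exact 95% CI 4.7% to 37.4%. There was one nail reoperation, 1/26 = 3.8%, with no reason given.

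Two assumptions are needed. The 4.5 months must bound each patient's follow-up, so that all four fell before six months. Because the procedures are not stated, k = 0 to 4 of them are taken as conversions or exchanges that the row would leave out.

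| k left out | Ex-fix rate | Fisher p, nail 1/26 | Fisher p, nail 0/26 |
|---|---|---|---|
| 0 | 9/24 = 37.5% | 0.0040 | 0.0005 |
| 1 | 8/24 = 33.3% | 0.0094 | 0.0014 |
| 2 | 7/24 = 29.2% | 0.021 | 0.0035 |
| 3 | 6/24 = 25.0% | 0.045 | 0.0085 |
| 4 | 5/24 = 20.8% | 0.093 | 0.020 |

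The last column covers the case in which the nail event also drops.

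**The case against.** The best defence is that the text governs. It is specific and says outright that these conversions count. The all-cause definition has only two named exclusions, and Aim 1 and the null hypothesis agree with it. The table lists inclusions and never says that an earlier conversion is not an event; where it means to exclude something, as with auto-dynamization, it says so. On this reading the table merely illustrates.

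That is a workable reading and most of the wording supports it, but the protocol does not state it. The table is introduced as the place where the events are detailed. If six weeks governs, the row's six-month limit does nothing for the first conversion it names. Section 4.2 also refers to stricter reoperation criteria than the pilot used, which an adjudicator could take as support for the table.

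Three further points stand in part:

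- In the nail arm the implant-removal and infection rows will often bring text and table to the same answer, so the exposure is probably mainly in the ex-fix arm.
- The pilot's four delayed-union operations may have been bone grafts, which belong to another row. With the nail event kept, p exceeds 0.05 only if all four drop out.
- Adjudication puts each reoperation before a panel, so few cases should go unnoticed. But the panel applies section 4.1 and so inherits the conflict.

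**Conclusion.** The concern holds. Section 4.1 contains two counting rules for one operation in the primary endpoint, and the protocol does not say which applies. The contradiction rests on the wording alone and needs no assumption.

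Its effect on the trial cannot be computed, because no conversion frequency is given. What can be said is that each disputed event is worth about one percentage point in its arm, and that the pilot makes such events plausible. The pilot and power tables are illustrations under stated assumptions, not forecasts, and the sample size arithmetic itself is not wrong. The endpoint would cease to be all-cause reoperation only if the table were read as exhaustive, since its six-month limits on conversion, grafting and dynamization would then remove earlier operations. The point must be fixed because it leaves an arm-dependent ambiguity in the primary outcome.

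**What to change.** Reconcile the text and the table into one counting rule for conversions and exchanges, applied to both arms. Do this before any by-arm outcome is reviewed, or record in the amendment what had been seen when the rule was fixed.

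- Either state that the all-cause definition with its named exclusions governs and that the table only classifies event type, or rename the endpoint in Aim 1 and the null hypothesis to match the table.
- Say whether an ex-fix-to-nail conversion within six weeks is an event.
- Use one term for the time origin. Section 4.1 counts variously from definitive stabilization, the index procedure and the index surgery. These may differ where a temporary fixator is placed first under damage control (section 5.5).
- Give the rule to the adjudicators and re-check every conversion or exchange already adjudicated.

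This concerns what is counted, not when any procedure is offered. The cost is a short amendment and a re-check of the few affected events, if any. No extra patients or visits are needed.

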5.1 Screening

Screening for patients will begin on December 14, 2015 at 9am and end in approximately one year when the appropriate sample size has been reached. All open tibia fractures arriving at the MOI emergency room during the enrollment period will be screened for inclusion in the study. All patients, even those who are excluded, need to have their information recorded on REDCAP.

The orthopedics department has been directed to call the study phone whenever an open tibia patient comes in. The research coordinator is required to keep the study phone close with them at all times.

- If the patient arrives during normal business hours (7am to 5pm), the coordinator will go to the emergency room to assist the patient's physician with screening. The coordinator is also expected to periodically check the emergency room for any new open tibia patients in case the emergency staff fail to contact the study phone.
- The study coordinator on duty will remain at MOI until 9pm and periodically check the emergency room for any new open tibia admissions. If the patient arrives from 9pm to 11pm, the coordinator will screen from home using the study laptop. If the patient meets study inclusion/exclusion criteria, the coordinator will come to the hospital to consent the patient to enroll in the study.

Inclusion Criteria

1. Skeletal maturity
2. AO/OTA 42 open tibia fractures *
3. Wound primarily closeable (no flap or delay in closure due to contamination needed)
4. Palpable pedal pulses (no vascular injury sustained)
5. Presentation within 24 hours from injury **

Exclusion Criteria

1. Current injury is a pathologic fracture
2. Sustained bilateral tibia fracture
3. Sustained comminuted femur fracture
4. Sustained severe Traumatic Brain Injury (GCS<12) ***
5. Sustained severe spinal cord injury (lower extremity paresis/paralysis)
6. Sustained severe burns (>10% total body surface area (TBSA) or >5% TBSA with full thickness or circumferential injury)
7. Prior ipsilateral leg injury requiring surgery
8. Prior or current lower limb deformity or abnormality
9. Unable to complete follow-up visits

* See addendum for OTA42 subclassification schematic

** Patients who present greater than 24 hours after injury and/or have non-primarily closeable wounds but meet all other criteria are eligible for the cohort study (see below)

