5.7 Definitive Treatment

Nail: It is up to the surgeon’s discretion as to the appropriate size of the nail. A total of 4 screws will be placed – 2 proximal and 2 distal. These decisions will be recorded on REDCAP during the operation.

Exfix: Two Schanz screws will be placed proximally and two will be placed distally; only a single bar will utilized. The patient will be instructed on proper pin-care procedures at the time of discharge which involves pouring methylated spirit (alcohol) directly onto the pins twice daily until the exfix is removed. The patient will be discharged with bandages covering the wound, but the pin insertion sites will be left open to allow for proper ventilation and pin-care. The patient will be discharged with dressing covering the wound and pin sites. The exfix will remain on for 3 months. At the 3 month follow-up, the decision will be made to (1) remove ex-fix, (2) remove ex-fix and replace with cast, (3) delay exfix removal, or (4) other. Delayed removal or other will be submitted for adjudication review.

Wound Protocol

If the wound is dry at the 2 week wound check, the dressing will be removed. If the wound is still wet at 2 weeks, the dressing will be changed and the patient will be instructed to periodically revisit the hospital to change the dressing until the wound becomes dry.

Weight Bearing Protocol

All patients will be advised to be on toe-touch status for the first 6 weeks. Afterwards, the patient will be instructed to bear weight as permitted by pain.

Summary of Treatment Options

Primarily closeable?	->	No	->	Cohort Study
	->	Yes (Cohort) (+ damage control)	->	Temporary exfix
	->	Yes (Cohort) (no damage control)	->	Definitive operation
	->	Yes (RCT): Nail (+ damage control)	->	Temp exfix (then nail)
	->	Yes (RCT): Exfix (+ damage control)	->	Temp exfix (then exfix)
	->	Yes (RCT): Nail (no damage control)	->	Nail now
	->	Yes (RCT): Exfix (no damage control)	->	Exfix now

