What is the surgical complication? <small>* must provide value</small>	 Superficial Surgical Site Infection  Deep Surgical Site Infection  Delayed Wound Healing  Nonunion/Delayed Union  Malignancy/Malunion  Hardware Failure (Non-infectious)  Missed Interlock  Compartment Syndrome  Other/Multiple 
Describe the details of the complication <small>* must provide value</small>	 
Upload any relevant images here (if available):	Upload document
Is reoperation being considered for this complication? <small>* must provide value</small>	 Yes  No 
Which hospital will the reoperation be performed at?	
ESTIMATED date of reoperation	   Format is DD-MM-YYYY. Insert date manually, by clicking on the calendar image above, or press "Today" if applicable

Has the reoperation been performed?

* must provide value

No
 Yes
 The patient no longer needs a reoperation

reset

This patient will now appear on the "Awaiting Reoperations" report. After the reoperation, change the answer to the above question to "Yes"

ACTUAL date of reoperation

Describe the reoperation that was performed:

Complication #1 Review

Has this issue been reviewed?

* must provide value

Yes
 No

reset

This issue needs to be reviewed.

Date of Review

Format is DD-MM-YYYY. Insert date manually, by clicking on the calendar image above, or press "Today" if applicable

Results of Review

* must provide value

- c. Additional surgical complications beyond the third event should be recorded in free text entry box. Label the event # accordingly (Event #4...)

Additional Surgical Complications

If the patient has had more than 3 surgical complications, describe them here. Include the following information:

1. Date complication first diagnosed by physician
2. Details of complication

If reoperation is being considered:

3. Type of surgery planned
4. Hospital
5. Estimated date of reoperation
6. Actual date of reoperation

[Expand](#)

Is reoperation being considered for any of these complications?

Yes
 No

* must provide value

[reset](#)

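### Section 4.1 defines the primary endpoint as all-cause reoperation, but its event table is narrower and no rule says which one the adjudicators apply

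*Protocol*

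**What the plan says.** The opening sentence of 4.1 Outcomes defines the primary outcome as "composite, all-cause reoperation within one year of definitive skeletal stabilization, excluding bedside irrigation and debridement for superficial pin tract infections or planned ex-fix removal". The null hypothesis under Specific Aims uses the same concept: "There is no difference in the all-cause re-operation rate comparing reamed intramedullary nailing and external fixation". Aim 1 does too.

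4.1 then says that the events in the composite are those detailed in a table. The table has seven rows:

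- The infection or hematoma row reads "Repeat incision and debridement or drainage for superficial or deep infection or hematoma following initial wound healing".
- Bone grafting, implant conversion or exchange, and nail dynamization each count only when more than 6 months have passed since index surgery.
- Implant removal, osteotomy and amputation carry no time limit.

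The prose above the table has its own conversion rule. Ex-fix-to-nail conversion counts as a reoperation once more than six weeks have passed since the index procedure. Nail-to-ex-fix conversion counts at any time.

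The complications form in 6.6 lists compartment syndrome, delayed wound healing and "Missed Interlock" among the surgical complications, and asks whether a reoperation is being considered. Under 5.10 Adjudication Review, three steering committee members vote on whether such an event is a primary outcome.

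**The concern.** An all-cause endpoint with two named exclusions and a list of qualifying events with timing conditions are different estimands. The protocol uses the first for its aim, its hypothesis and the name of the endpoint, and the second for the detail of what counts.

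If adjudicators follow the table, the trial will report as all-cause a rate that omits some unplanned returns to theatre. If some follow the prose and others the table, identical patients will be coded differently. The steering committee that votes also evaluates interim data (Study Steering Committee), so the definition should not be settled case by case in those votes.

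**Working it through.** **The plan's own figure.** Section 4.2 gives 88 per group for 5% versus 20%, alpha 0.05, power 80%. With p̄ = 0.125 and d = 0.15, two-sided:

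- n₀ = [1.960·√(2·0.125·0.875) + 0.842·√(0.20·0.80 + 0.05·0.95)]² / 0.15² = (0.917 + 0.383)² / 0.0225 ≈ 75.1
- Continuity-corrected: n = (n₀/4)·[1 + √(1 + 4/(n₀·d))]² = 18.78 × (1 + 1.164)² ≈ 87.9, which rounds up to 88.

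The sample size is reproduced and is not in dispute.

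**The two definitions applied to the same cases.** All cases fall within one year of definitive stabilization.

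| Operation on the study limb | Opening prose of 4.1 | Primary Events table |
|---|---|---|
| Debridement in theatre for infection before the wound has healed | Event | Not an event |
| Repeated debridement of an infected wound that never heals | Event | Never an event in that row |
| Surgery for compartment syndrome | Event | No row |
| Surgery for wound breakdown | Event | No row |
| Return to theatre for a missed interlock | Event | No row |
| Bone grafting or dynamization at 5 months | Event | Not an event (6-month limit) |
| Ex-fix-to-nail conversion at 3 months to obtain union | Event (beyond six weeks) | Not an event in the conversion row (6-month limit) |
| Amputation | Event | Event |

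**Extent of the gap.**

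- Four of the seven rows carry a timing condition: one depends on wound healing and three on 6 months. For those three rows, about the first half of the one-year window is not counted.
- For ex-fix-to-nail conversion, the follow-up schedule sets 42 days for 6 weeks and 182 days for 6 months. Prose and table therefore disagree over about 182 − 42 = 140 days, or 20 weeks.
- 4.1 does not define when a wound has initially healed, although 5.7 expects some wounds to be slow: "If the wound is still wet at 2 weeks, the dressing will be changed".

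**The healing clause in the randomized trial.** Randomization takes place only after the surgeon judges that the wound can be closed primarily (5.4, 5.6). A later debridement for infection is then normally an unplanned complication. The clause therefore does more than set aside planned staged debridement.

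**Why no effect on power follows.** Suppose, as an assumption, that the table drops 2/9 of events in both arms. That is the infection share of the pilot's ex-fix reoperations.

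- If 20% and 5% are true all-cause rates, the counted rates are 20 × 7/9 = 15.6% and 5 × 7/9 = 3.9%. Power at 88 per group is 74.7%, against 85.9% at the design rates (both without continuity correction).
- If 20% and 5% are already table-restricted, the all-cause rates are 20 ÷ (7/9) = 25.7% and 5 ÷ (7/9) = 6.4%. Power for the all-cause endpoint is 94.3%.

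The protocol does not say which case applies.

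**The case against.** **The narrowing may be intended.** Section 4.2 says the design rates were made more conservative partly because the criteria for reoperation would be stricter than in the pilot. The 6-month limits also match the definition of non-union in 4.1. This stands as a reason why a restricted list may be legitimate. It does not justify calling that list all-cause.

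**Adjudication could resolve each case.** The vote can go either way, so one cannot say that early infections will be read as successes. A reader might infer that, but it holds only if the table is a closed list that overrides the sentence defining the endpoint. Even then some early failures count: amputation and nail removal to facilitate union have no time limit, and nail-to-ex-fix conversion counts at any time. Compartment syndrome and both grades of infection are also reported as secondary outcomes. What remains is that 5.10 gives no rule for the vote.

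**The healing clause may have a purpose.** Damage control with later definitive surgery is allowed for randomized patients (5.5), so planned returns to theatre do occur. That stands, and an explicit exclusion of planned staged surgery deals with it.

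**The pilot does not measure the loss.** A reader might take the nine ex-fix reoperations, "2 for deep infection, 3 for malalignment, 4 for delayed union", and conclude that the counted rate could fall from 9/24 = 37.5% to 3/24 = 12.5%. The documents do not support that range:

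- The four delayed-union operations are not described. If they were conversions to a nail after six weeks, the prose counts them.
- The timing of the two infection reoperations is not given.
- The three malalignment cases were revised, but not necessarily by osteotomy, which is the only malalignment procedure in the table.

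**No direction of bias.** A reader might infer a pull toward no difference. That needs one arm to have more early uncounted failures, and the pilot found no significant difference in wound healing or deep infection (7.7% nail, 12.5% ex-fix).

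**Conclusion.** The concern holds as an unresolved contradiction in the definition of the primary endpoint. One text says all-cause with two exclusions. The other adds a healing condition, three 6-month limits and a list without rows for several complications that the protocol's own form records. The two also disagree for about 20 weeks on ex-fix-to-nail conversion. Which patients count depends on which text is applied, and nothing in 4.1 or 5.10 decides it.

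This rests on the wording alone and needs no assumption about event rates. The number of reclassified patients, the direction of any bias and any loss of power cannot be derived from the protocol and are not claimed. The sample size of 88 per group is correct for its stated inputs.

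**What to change.** State in 4.1, and repeat in the adjudication instruction in 5.10, which text governs.

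**Preferred: the all-cause definition governs and the table gives examples.**

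- Delete the wound-healing condition from the infection row.
- Count any unplanned return to theatre on the study limb that is related to the fracture, wound or implant. Count from definitive stabilization to one year, so that the clock is right for damage-control patients.
- Exclude only the two operations already named in the prose, plus planned staged or damage-control surgery.
- Report the time-restricted table version as a sensitivity analysis.

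**Alternative: the narrower list is what was meant.** Remove the term all-cause from Aim 1, the null hypothesis and 4.1, name the endpoint as the listed events, and say that the list is closed.

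**In either case** reconcile the six-week and 6-month rules for counting ex-fix-to-nail conversion. State that the reconciled rule takes precedence over any general clause, so that such a clause does not bring in the conversions within six weeks that the prose implies are not events. This concerns outcome counting only, not when a conversion should be done.

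The cost is an amendment to one table and one instruction, and any event already voted on should be re-read against the settled rule. The complications form in 6.6 already records the complication, the reoperation and its date. The small downside of the preferred option is that a few minor early returns to theatre will count as events.
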